I have read and understand the contents of this clinical protocol for Study No. KCP-9274-901 dated 11 March 2020 and will adhere to the study requirements as presented, including all statements regarding confidentiality. In addition, I will conduct the Study in accordance with current Good Clinical Practice, ICH E6, and applicable FDA regulatory requirements.

Printed Name of Investigator

[figure not shown]
Signature of Investigator

Institution

Date

PROTOCOL SYNOPSIS

Sponsor: Karyopharm Therapeutics Inc.	Investigational Product: KPT-9274	Study Phase: Phase 1
Title of Study: A Phase 1 Open-Label Study of the Safety, Tolerability and Efficacy of KPT-9274, a Dual Inhibitor of PAK4 and NAMPT, in Patients with Advanced Solid Malignancies or Non-Hodgkin's Lymphoma		
Study Name: PANAMA: PAK4 and NAMPT in Patients with Solid Malignancies or NHL		
Name of Active Ingredient: (E)-3-(6-aminopyridin-3-yl)-N-((5-(4-(4,4-difluoropiperidine-1-carbonyl)phenyl)-7-(4-fluorophenyl)benzofuran-2-yl)methyl)acrylamide		
Protocol Number: KCP-9274-901		
Study Center(s): Multi-center		
Patient Population: Patients with advanced solid malignancies (including sarcoma, colon, lung, etc.) or non-Hodgkin's lymphoma for which all standard therapeutic options considered useful by the investigator have been exhausted and with progressive disease on study entry.		
Objectives and Endpoints: This study will evaluate the safety, tolerability, and efficacy of oral KPT-9274 for the treatment of patients with advanced solid malignancies or non-Hodgkin's lymphoma (NHL).		
Objectives	Endpoints	
Primary		
Parts A and B 
• To assess the maximum tolerated dose (MTD) in each Part• To establish a recommended phase 2 dose (RP2D)	Parts A and B 
• MTD/RP2D• Dose limiting toxicities (DLTs)• The occurrence of Grade ≥ 3 adverse events (AE), all serious adverse events (SAEs), and all AEs leading to treatment discontinuation	
Dose Expansion (if conducted) 
• Preliminary evidence of anti-tumor activity of KPT-9274 at the RP2D \pm niacin ER	Dose Expansion (if conducted) 
• Overall response rate (ORR), duration of response (DOR), disease control rate (DCR), duration of disease control, progression-free survival (PFS), overall survival (OS), time to progression (TPP)	

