At least 1 clinical response (minimum of stable disease ~16 weeks) must be seen in any of the first 10 patients treated at the RP2D in order to fully enroll either expansion cohort. These 10 patients include the patients enrolled under the 3+3 design for DLT assessment; if necessary, additional patients will be enrolled to a maximum of 10 patients. If no clinical responses are observed, the study will be stopped for futility. If a clinical response is observed at any time, then enrollment of the full expansion cohort may proceed. Initiation of the KPT-9274 + niacin ER escalation will not be dependent upon demonstration of clinical benefit of the single agent, but futility at the KPT-9274 + niacin ER RP2D will be assessed prior to full expansion using the same criterion as described above for the single agent KPT-9274.

The KPT-9274 ± niacin ER expansion cohort will consist of 4 groups of approximately 45 patients (please note that these expansion groups may change based on escalation results) including:

- I. NAPRT1 deficient tumor group, approximately 10 patients
- II. NAPRT1 positive tumor group, approximately 10 patients
- III. Either NAPRT1 deficient or positive tumor group, approximately 10 patients
- IV. IDH1 mutant tumor group, approximately 15 patients

Please note that the composition of the expansion groups (e.g., number of patients with NAPRT1 positive vs NAPRT1 deficient tumors) may change based on the results from the escalation phase. An additional, optional KPT-9274 single agent expansion cohort will consist of ~ 20 patients with any tumor mutational status.

Patients in the Dose Expansion Phase may be treated with the RP2D of KPT-9274 ± niacin ER according to the same schedule administered in the Dose Escalation Phase of the study.

Patients who are in Part A or Part B of the Dose Escalation Phase being treated at the RP2D ± niacin ER dose chosen for expansion will be included in the efficacy and safety analyses of the Dose Expansion Phase.

Part C: KPT-9274 + Nivolumab

After sufficient data from Part A is available, Dose Finding with the potential for Expansion in patients with melanoma will be conducted to further explore safety, tolerability and preliminary evidence of anti-tumor activity of the RP2D (or any DLT-cleared dose) of KPT-9274 + nivolumab.

DOSE FINDING PHASE

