Investigational or commercial anticancer agents other than KPT-9274 are not allowed during the study. The initiation of any non-protocol specific anti-tumor treatment is considered an indication of disease relapse/progression and should be recorded appropriately in the eCRFs.

There are exceptions including localized palliative radiation, hormonal therapy for patients with prostate cancer, hormonal contraception for the prevention of pregnancy, and blood products/growth factors. For other possible cases, consult the Karyopharm Medical Monitor.

Treatment Duration:

Treatment cycles are 28 days long. A patient may continue to receive KPT-9274 ± niacin ER (Parts A and B) or KPT-9274 + nivolumab (Part C) until the patient experiences progressive disease, withdraws consent or decides to withdraw from further treatment, is lost to follow-up, experiences intolerable toxicity which precludes further treatment with KPT-9274, or treatment is discontinued at the discretion of the Investigator or the Karyopharm Medical Monitor.

Criteria for Evaluation:

Safety Endpoints:

The safety and tolerability of KPT-9274 ± niacin ER as well as KPT-9274 + nivolumab will be evaluated by means of DLTs, AE reports, physical examination results, electrocardiogram results and laboratory safety evaluations. The National Cancer Institute (NCI) Common Terminology Criteria for Adverse Events (CTCAE), Version 4.03, will be used for grading of AEs.

A DLT is defined as an AE or abnormal laboratory value that occurs within the first 28 days of treatment with KPT-9274, except for those that are clearly and incontrovertibly due to underlying disease, disease progression, or extraneous causes, and meets any of the criteria for defining dose-limiting toxicities.

Efficacy Endpoints:

The secondary endpoint of disease response will be evaluated according to RECIST 1.1¹ (advanced solid malignancies) or Lugano Classification² (NHL) and will include the following:

- **Overall response rate (ORR):** ORR = proportion of patients who have a response of partial response (PR) or complete response (CR)
- **Duration of response (DOR):** the duration of time from first meeting CR or PR measurement criteria (whichever occurs first) until the first date that PD recurrence is objectively documented.
- **Disease control rate (DCR):** DCR = proportion of patients who have a response of CR, PR, and Stable Disease (SD) ≥ 16 weeks.

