APPENDIX 4. RECIST VERSION 1.1

(Modified from [Eisenhauer 2009](#))

All patients will have their BEST RESPONSE on study classified as outlined below:

Complete Response (CR)

Disappearance of all target lesions. Any pathological lymph nodes (whether target or non target) must have reduction in the short axis to <10mm.

Partial Response (PR)

At least a 30% decrease in the sum of diameters of target lesions, taking as reference the baseline sum diameters.

Stable Disease (SD)

Steady state of disease. Neither sufficient shrinkage to qualify for PR nor sufficient increase to qualify for PD.

Progressive Disease (PD)

At least a 20% increase in the sum of diameters of measured lesions taking as references the smallest sum of diameters recorded since the treatment started. In addition to the relative increase of 20%, the sum must also demonstrate an absolute increase of at least 5 mm.
Appearance of one or more new lesions will also constitute progressive disease.

Response Duration

Response duration will be measured from the time measurement criteria for CR/PR (whichever is first recorded) are first met until the first date that recurrent or progressive disease is objectively documented, taking as reference the smallest measurements recorded since the treatment started.

Stable Disease Duration

Stable disease duration will be measured from the time of start of therapy until the criteria for progression are met, taking as reference the smallest measurements recorded since the treatment started.

Evaluation of Best Overall Response – Patient with Target (= non-target) disease

Target lesions	Non-Target lesions	New Lesions	Overall response
CR	CR	No	CR
CR	Non-CR-Non-PD	No	PR
CR	NE	No	PR
PR	Non-PD/or not all evaluated	No	PR
SD	Non-PD/or not all evaluated	No	SD

Target lesions	Non-Target lesions	New Lesions	Overall response
Not all evaluated	Non-PD	No	NE
PD	Any	Yes or No	PD
Any	PD	Yes or No	PD
Any	Any	Yes	PD

Evaluation of Best Overall Response – Patient with Non-Target Disease

Non-Target lesions	New Lesions	Overall response
CR	No	CR
Non-CR-Non-PD	No	Non-CR/Non-PD ¹
Not all evaluated	No	NE
Unequivocal PD	Yes or No	PD
Any	Yes	PD

Note: Patients with a global deterioration of health status requiring discontinuation of treatment without objective evidence of disease progression at that time should be reported as “*symptomatic deterioration*”. Every effort should be made to document the objective progression even after discontinuation of treatment.

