# 4.1. EFFICACY ENDPOINTS

Please refer to Table 4-1 below for primary and secondary endpoints and the corresponding definitions

Table 4-1 Efficacy Endpoints and Definitions

Endpoint	Definition	
Secondary Endpoints		
Objective response rate (ORR)	Proportion of patients who have a response of partial response (PR) or complete response (CR)	
Duration of response (DOR)	The duration of time from first meeting CR or PR measurement criteria (whichever occurs first) until the first date that PD recurrence is objectively documented or death due to any cause	
	Please refer to Table 4-3 for details on the outcome and censoring definitions.	
Progression-free survival (PFS)	The duration of time from date of first study treatment until the first date that PD is objectively documented or death due to any cause.	
	Please refer to Table 4-2 for details on PFS outcome status (PFS event vs. censored) and censoring definitions.	
Overall survival (OS)	Duration from the date of first study treatment until death due to any cause. If death event did not occur during the follow-up period, the patient is censored at the date of discontinuation from the study (i.e. withdrawal of consent), or date of last participating visit (e.g., a telephone contact with patient status being alive) on or before database cutoff date, whichever occurs first.	
Time to Progression (TTP)	The duration of time from date of first study treatment until the first date that PD is objectively documented or death due to PD	

Disease control rate (DCR)	Proportion of patients who have a response of CR, PR, and Stable Disease (SD) ≥ 16 weeks.
Duration of disease control	Duration of disease control is defined among patients achieving disease control as the duration from the date of first meeting the response measurement criteria for disease control to the date of PD or death due to disease progression.  Please refer to Table 4-3 for details on the outcome and censoring definitions.

Table 4-2 PFS and DOR outcome and censoring definition

Situation	Date of event or censoring	Outcome
No baseline disease assessment	Date of first study treatment	Censored
No adequate post-baseline disease status assessment unless death occurs prior to first post-baseline assessment	Date of first study treatment	Censored
Death before PD without a gap of 2 or more consecutively missed scheduled disease status assessment before death	Date of death	Event

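### For RECIST-assessed patients, ORR and the DOR built on it accept a response seen on one scan only; confirmed and unconfirmed ORR should be reported side by side.

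*Protocol*

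**What the plan says.** The synopsis (Efficacy Endpoints) defines "ORR = proportion of patients who have a response of partial response (PR) or complete response (CR"). Protocol 2.2.2 and 9.5 and SAP 1.3.1 carry the same definition, and SAP Table 4-1 has "Proportion of patients who have a response of partial response (PR) or complete response (CR"). Appendix 4, headed as modified from the RECIST 1.1 publication, states "All patients will have their BEST RESPONSE on study classified as outlined below". Its PR criterion is "At least a 30% decrease in the sum of diameters of target lesions, taking as reference the baseline sum diameters", and its response tables contain no confirmation step. DOR is "the duration of time from first meeting CR or PR measurement criteria (whichever occurs first") up to progression, so one scan starts a response.

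Solid-tumour scans are repeated every 8 weeks until progression or end of treatment (protocol 7.3.3.1), with no cap on their number.

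Two rules come close, and neither confirms a response by imaging. Protocol 7.3.2.2 allows a discretionary marrow biopsy to confirm CR or PR in NHL patients with known marrow involvement. SAP 1.5 refers to confirmed PD when describing how long treatment continues.

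The synopsis table of objectives lists "Overall response rate (ORR), duration of response (DOR), disease control rate (DCR") and the time-to-event measures as primary endpoints of the Dose Expansion Phase, if it is conducted. The synopsis text on efficacy endpoints and SAP Table 4-1 call disease response secondary. ORR is analysed by a point estimate and an exact 95% CI (SAP 4.2), with no test and no reference rate.

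**The concern.** A tumour whose true change is short of -30% can still read below -30% on one scan. Best response over all scans keeps that one low reading and discards the others, so the chance of a false PR grows with the number of scans. A misread cannot cancel out across patients, because nothing in the classification takes a response back once it has been recorded.

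The study is open-label with no control arm (protocol 6.1.4 and 6.7), so there is no comparator in which the same error would appear. The expansion groups are planned at about 10, 10, 10 and 15 patients. One false responder moves a group's ORR by 1/15 = 6.7 to 1/10 = 10 percentage points. The exact CI describes sampling error only and does not cover misclassification.

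DOR inherits the problem. A patient with one falsely low scan enters the DOR analysis, and the low reading also becomes the smallest sum from which progression is measured.

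**Working it through.** The documents give no expected ORR, error rate or power for this endpoint, so there is no plan figure to reproduce.

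**Inputs from the documents.** PR at -30% from baseline; PD at "At least a 20% increase in the sum of diameters of measured lesions", measured from the smallest sum, with at least 5 mm absolute increase (Appendix 4); scans every 8 weeks.

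**Assumptions not in the documents.** Independent reading error on the log scale with SD s = 5%, 10% or 15% at each scan, including baseline. No true responders. True change d uniform from -25% to +20% and constant over scans. Two or three post-baseline scans. The 5 mm condition does not bind.

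**Step 1: one scan, unchanged tumour.** The observed ratio to baseline is exp(e_t - e_0), so P(false PR) = Φ(ln 0.70 / (s√2)), with ln 0.70 = -0.357.
- s = 5%: Φ(-0.357/0.0707), about 0%
- s = 10%: Φ(-0.357/0.141) = Φ(-2.52), about 0.6%
- s = 15%: Φ(-0.357/0.212) = Φ(-1.68), about 4.6%

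**Step 2: a mix of stable tumours over several scans.** Observed change = exp(ln(1+d) + e_t - e_0) - 1, simulated for 1,000,000 patients. The table gives false ORR.

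| Reading SD | Any single scan, 2 / 3 scans | Two consecutive scans, 2 / 3 scans |
|---|---|---|
| 5% | 1.8% / 2.4% | 0.3% / 0.5% |
| 10% | 8.3% / 10.5% | 2.0% / 2.9% |
| 15% | 16.0% / 20.2% | 4.3% / 6.1% |

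Stopping follow-up at measured PD changes little: at s = 10%, 8.3% / 10.4% against 1.9% / 2.8%.

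**Step 3: scale to the population.** These figures apply to truly stable patients. If a share p truly progresses and contributes no false PR, multiply by (1 - p). With p = 50% as an illustration, 8.3% becomes 0.5 × 8.3% = 4.2%.

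**Step 4: the price of confirmation.** The same error model, with follow-up stopped at measured PD, applied to true responders at s = 10%:
- true change -35%: 84% counted on a single scan against 52% confirmed (2 scans); 90% against 61% (3 scans)
- true change -40%: 95% against 72% (2 scans)

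Confirmation therefore removes most false responses and also loses true ones near the threshold.

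**The case against.** **The size rests on assumed inputs.** This stands. Reading SD and the distribution of true change are not in the documents, and entry requires progressive disease, so many patients may truly progress. The direction of the error in stable tumours does not depend on these inputs. The documents do not say who reads the scans, so nothing here assumes investigator reading.

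**Confirmation brings its own bias.** This also stands, as Step 4 shows. Confirmed ORR should therefore not simply replace the unconfirmed rate.

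**The cited RECIST guideline may settle the matter.** The documents alone cannot show this. Appendix 4 is a modified extract, and the plan should state which rate it reports.

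**ORR is only descriptive, in an expansion that may not happen.** True, and it limits the weight of the point.

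**A reader might infer that DCR and the futility rule are inflated too.** The documents do not support that.
- SD of at least 16 weeks already counts in DCR, so a durably stable tumour misread as PR changes nothing. The only added route is a false PR at week 8 followed by PD at week 16. In the Step 2 model that is 0.04% to 4.6% of patients across the SD range.
- The +20% PD threshold is nearer than -30%, so error in unchanged tumours mostly produces false PD. Measured DCR by week 16 is 98.6%, 77.1% and 60.9% at SD 5%, 10% and 15%, against a true 100%. The net error is downward.
- The futility rule reads "At least 1 clinical response (minimum of stable disease ~16 weeks) must be seen in any of the first 10 patients". Durable SD passes it without any PR. Section 6.2.7 sets about 8 weeks instead, and under that wording any first scan without PD passes.
- At SD 10%, the chance of at least one false PR among ten stable patients is 1 - (1 - 0.083)^10 = 58% over two scans and 1 - (1 - 0.105)^10 = 67% over three. These are not probabilities of wrongly opening the expansion. In that model all ten patients truly have stable disease, and at least one passes in over 99.99% of cases with or without confirmation.

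**Conclusion.** The point holds for ORR and for the DOR built on it, in patients assessed by RECIST. Followed as written, the plan counts some misread stable tumours as responders, and the uncontrolled design offers no way to see how many. If all patients are truly stable with change uniform from -25% to +20% and reading SD is 5% to 15%, false ORR over two to three scans is about 2% to 20% on the single-scan rule. With two consecutive scans it is about 0.3% to 6%. The real figures are lower in proportion to the share who truly progress. The calculation uses size criteria only and says nothing about Lugano or PET-based response.

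This is a cheap improvement to the reporting of a descriptive endpoint. It does not show that DCR or the futility rule is biased upward, and it gives no reason to add a confirmation requirement to protocol 9.5.1.

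**What to change.** In SAP Table 4-1 and protocol 9.5, for RECIST-assessed patients:
- Define best overall response explicitly.
- For the Dose Expansion Phase, report confirmed ORR with its exact 95% CI. Confirmed means that the CR or PR criteria are still met at the next scheduled 8-week scan.
- Always show unconfirmed ORR beside it.
- Report DOR for confirmed responders, starting at the first of the two scans.

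The scans are already scheduled, so the cost is wording and programming. The downside is that confirmed ORR is lower. It misses some true responders near -30% (for a true -35% change at 10% SD, about 52% counted against 84% over two scans) and patients who stop after one responding scan. Showing both rates keeps these patients visible.

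Separately, the duration of stable disease in the futility rule is about 8 weeks in protocol 6.2.7 but about 16 weeks in the synopsis, protocol 9.5.1 and SAP 1.1. These passages must be reconciled.

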Table 20: Classification of Adverse Events by Causality	100
Table 21: ECOG Performance Status Scale.....	115
Table 22: Criteria for Involvement of Site.....	116
Table 23: Revised Staging System for Primary Nodal Lymphomas	117
Table 24: Revised Criteria for Response Assessment	118

LIST OF FIGURES

Figure 1: Study Flow Chart.....	34
---------------------------------	----

LIST OF ABBREVIATIONS AND DEFINITIONS OF TERMS

The following abbreviations and specialist terms are used in this study protocol.

Table 9: Abbreviations and Definitions of Terms

Abbreviation or Specialist Term	Explanation
°C	degrees Celsius
°F	degrees Fahrenheit
AE	adverse event
ALT	alanine aminotransferase
AML	acute myeloid leukemia
ANC	absolute neutrophil count
AST	aspartate aminotransferase
AUC	area under the curve
B-ALL	B-cell acute lymphoblastic leukemia
BP	blood pressure
BSA	body surface area
CBC	complete blood count
CBR	clinical benefit rate
CI	confidence interval
CL/F	plasma clearance
C _{max}	maximum plasma concentration
cm	centimeter
CNS	central nervous system
COX-2	cyclooxygenase-2
CR	complete response
CrCl	creatinine clearance
CSR	clinical study report
CT	computed tomography
CTCAE	Common Terminology Criteria for Adverse Events
CXDX (e.g., C1D1)	Cycle X Day X (e.g., Cycle 1 Day 1)
DAP	Data Analysis Plan
DCR	disease control rate
DDA	deoxyribonucleic acid damaging agent
DLT	dose-limiting toxicity

Abbreviation or Specialist Term	Explanation
DNA	deoxyribonucleic acid
DOR	duration of response
DSMB	Data Safety Monitoring Board
ECG	electrocardiogram
ECOG	Eastern Cooperative Oncology Group
eCRF	electronic case report form
EORTC QLQ	European Organization for Research and Treatment of Cancer Quality of Life Questionnaire
EoT	end of treatment
ER	extended release
FACT-G	Functional Assessment of Cancer Therapy
FACT-Lym	Functional Assessment of Cancer Therapy-Lymphoma
FDA	Food and Drug Administration
FISH	fluorescence in situ hybridization
FLC	free light chain
GCP	Good Clinical Practice
G-CSF	granulocyte-colony stimulating factor
GI	gastrointestinal
GLP	Good Laboratory Practice
GM-CSF	granulocyte macrophage-colony stimulating factor
HAT	hormone ablation therapy
Hb	hemoglobin
HBsAg	hepatitis B virus surface antigen
HBV	hepatitis B virus
hCG	human chorionic gonadotropin
HCV	hepatitis C virus
HDPE	high-density polyethylene
HIV	human immunodeficiency virus
HNSTD	highest non-severely toxic dose
HPLC/MS-MS	high performance liquid chromatography/tandem mass spectrometry
hr	hour
IB	Investigator's Brochure

Abbreviation or Specialist Term	Explanation
IC ₅₀	50% inhibitory concentration
ICF	informed consent form
ICH	International Conference on Harmonization
IDH1	isocitrate dehydrogenase 1 (NADP ⁺), soluble
IHC	immunohistochemistry
INR	International normalized ratio
IRB	Institutional Review Board
ITT	intent-to-treat
IV	intravenous
Karyopharm	Karyopharm Therapeutics Inc.
kg	kilogram
LLN	lower limit of normal
LVEF	left ventricular ejection fraction
MDR	multiple drug resistance
mIU	milli-international units
mL	milliliter
MM	multiple myeloma
MRI	magnetic resonance imaging
CCI	
MTD	maximum tolerated dose
MUGA	multiple gated acquisition
N	number of patients
NAD	nicotinamide adenine dinucleotide
NAMPT	nicotinamide phosphoribosyltransferase/PBEF/visfatin
NAPRT1	nicotinate phosphoribosyltransferase
NCI	National Cancer Institute
NHL	non-Hodgkin's lymphoma
Niacin	vitamin B3/nicotinic acid
NSAID	non-steroidal anti-inflammatory drug
ORR	overall response rate
OS	overall survival
OTC	over the counter

Abbreviation or Specialist Term	Explanation
PAK4	p21 protein (Cdc42/Rac)-activated kinase 4
CCI	
PD	progressive disease
CCI	
PET	positron emission tomography
PFS	progression-free survival
PK	pharmacokinetic(s)
PP	per protocol
PPI	proton pump inhibitor
PR	partial response
CCI	
QOD	every other day
QoL	quality of life
CCI	
RAS	rat sarcoma viral oncogene homolog
RBC	red blood cell
RECIST	Response Evaluation Criteria in Solid Tumors
RNA	ribonucleic acid
RP2D	Recommended Phase 2 Dose
SAE	serious adverse event
SAP	Statistical Analysis Plan
SD	stable disease
SUSAR	suspected unexpected serious adverse reaction
$t_{1/2}$	terminal plasma half-life
TEAE	treatment-emergent adverse event
t_{max}	time to peak plasma concentration
TNM	tumor nodes metastasis
TOI	trial outcomes index
TSH	thyroid stimulating hormone
TPP	time to progression
ULN	upper limit of normal
V_d/F	volume of distribution

Abbreviation or Specialist Term	Explanation
WBC	white blood cell

